7. STUDY ASSESSMENTS AND PROCEDURES

7.1. Schedule of Events and Study Parameters

Table 1: Schedule of Events for Trial Phase

Visit	1	2	3	4	5	6	7	8	9
Type of Visit (In-Person or Phone)	In-Person	In-Person	In-Person	In-Person	Phone	In-Person	Phone	Phone	In-Person
Visit Window ^a	W-10 to -2	BL W-1	Dosing Day (D1) ^c	Disc (D3)	W2	W3	W4	W6	W8
Screening ^b	±3D			+4D	±2D	±3D	±2D	±2D	±3D
Informed consent	X								
Inclusion/exclusion criteria	X	X							
Genetic testing ^{d,e,f}	X								
Demography	X								
Medical history	X								
COVID-19 test ^g	X	X	X						
Pregnancy test ^h	X	X	X			X			X
AADC enzyme activity assessment ^f	X								
Collect CSF history ⁱ	X								
CSF neurotransmitter analysis ^{f,j,k}			X ^{j,m,o}						X ^{j,o}
Anti-AAV2 antibody (IgG and neutralizing titers) ^f	X		X ^l	X		X			X
Viral shedding (blood and urine) ^{f,n}			X ^l	X		X			X
Viral shedding (CSF) ^{f,j}			X ^{j,m,o}						X ^{j,o}
Physical examination ^p	X	X	X	X		X			X
Vital signs ^q	X	X	X	X		X			X
Height/weight	X	X	X	X		X			X
Brain MRI (T1-MPRAGE and T2-FLAIR sequences) ^{j,o}	X ^r			X ^s		X ^s			X ^s
Real-time intrasurgical MRI			X						
Postdose brain CT ^t			X						
Brain ¹⁸ F-DOPA PET ^{j,o,u}		X							X
Chest x-ray ^v		X							
12 lead ECG		X							

Visit	1	2	3	4	5	6	7	8	9
Type of Visit (In-Person or Phone)	In-Person	In-Person	In-Person	In-Person	Phone	In-Person	Phone	Phone	In-Person
Visit Window ^a	W-10 to -2	BL W-1	Dosing Day (D1) ^c	Disc (D3)	W2	W3	W4	W6	W8
	Screening ^b	±3D		+4D	±2D	±3D	±2D	±2D	±3D
Oculogyric crisis eDiary instructions for use ^w	X								
AADC-specific symptoms ^x	X	X		X		X			X
Laboratory tests ^y	X	X		X		X			X
T-cell sample collection	X		X	X		X			X
PDMS-2		X							
Bayley-III		X							
EQ-5D-Y ^z		X							
Study drug injection (eladocagene exuparovec)			X						
AEs		X	X	X	X	X	X	X	X
Concomitant medications		X	X	X	X	X	X	X	X

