^p Complete physical examination at Screening, Baseline Visit, and on Dosing Day (D1), and targeted physical examination for all other visits. The complete physical examination will consist of an examination of the following: neurological assessment and assessments of general appearance, any changes to feeding tube placement or removal, skin, head, eyes, ears, nose, throat, neck (including thyroid), lymph nodes, chest, heart, abdomen, and extremities. The targeted physical examination will consist of a neurological assessment, general appearance assessment, any changes to feeding tube placement or removal, and heart auscultation.

^q Vital signs include temperature, pulse, respiratory rate, and blood pressure.

^r Brain MRI with gadolinium performed at Screening to exclude subjects who may have pre-existing conditions.

^s Brain MRI with gadolinium to check for persistent CSF leakage/fistula and inflammatory changes (eg, aseptic ventriculitis/meningitis). An MRI should be performed immediately if a CSF leak is suspected.

^t Brain CT for postdose hemorrhage check should be performed within 6 hours after the end of surgery.

^u PET scans will be centrally read.

^v P-A and lateral chest x-ray.

^w Parent/caregiver must complete eDiary or paper diary for each OGC occurrence throughout the Trial Phase and Extension Phase. In the event that the eDiary cannot be used, a paper version will be provided.

^x Findings for AADC-specific symptoms will be collected at every in-person visit after D1. These assess for floppiness (hypotonia), limb and stimulus-provoked dystonia, and muscle power.

^y Laboratory tests (PT; PTT or aPTT; INR; CBC w/diff; and CMP analysis [including total bilirubin]). These will be assessed by a local laboratory.

^z The EQ-5D-Y will not be administered to subjects under 4 years of age. If the subject turns 4 during the study, the caregiver will complete the EQ-5D-Y per protocol after the subject turns 4.

Table 2: Schedule of Events for Extension Phase

Visit	10	11	12	13	14	15	16	17	18	19	20
Type of Visit (In-Person or Phone)	Phone	In-Person	Phone	Phone	In-Person	Phone	Phone	In-Person	Phone	Phone	In-Person
Visit Window ^a	W10 ±2D	W12 ±3D	W16 ±2D	W20 ±2D	W24 ±3D	W28 ±2D	W32 ±2D	W36 ±3D	W40 ±2D	W44 ±2D	W48/ET ^b ±3D
Pregnancy Test ^c		X			X			X			X
CSF neurotransmitter analysis ^{d,e,f}											X
Anti-AAV2 antibody (IgG and neutralizing titers) ^d		X			X			X			X
Viral shedding (blood and urine) ^{d,g}	X			X			X				X

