7.3.6. AADC-Specific Symptoms

Aromatic L-amino acid decarboxylase deficiency is characterized by specific neurological symptoms, including floppiness (hypotonia), oculogyric crisis (OGC) episodes, limb dystonia, and stimulus-provoked dystonia. These symptoms will be evaluated by the investigator as described in [Table 1](#), [Table 2](#), and [Table 3](#).

Detailed neurologic examinations, including assessments of muscle power, muscle tone, and spontaneous movement, will be performed as described in [Table 1](#) and [Table 2](#).

Any OGC episodes and associated concomitant medications will be recorded throughout the Trial Phase and Extension Phase by caregivers using an electronic diary (eDiary) with prespecified questions. In the event that the eDiary cannot be used, a paper version of the diary will be provided. Oculogyric crisis episodes should be entered in the eDiary or paper diary when they occur.

Muscle power will be measured in the following 4 areas: I (right upper extremity), II (left upper extremity), III (right lower extremity), and IV (lower left extremity). Muscle power is typically graded on a 6-point scale as follows:

- 1, no movement
- 2, trace of contraction
- 3, active movement when gravity is eliminated
- 4, active movement against gravity
- 5, active movement against gravity and resistance
- 6, normal strength

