4.3.1. Handling of Dropouts or Missing Data

Missing data due to missed visits or withdrawal or death will not be imputed.

In administering PDMS-2, the following instructions were provided in the PDMS-2 Manual:

- **Entry Points:** The entry points are marked on each subtest in the Examiner Record Booklet. The entry points were determined empirically to allow the examiner to begin testing on an item that 75% of children in the normative sample at that age passed. When testing children with known disabilities, the examiner should use clinical judgement to determine the most appropriate entry point.
- **Basal Level:** The basal level is established when the child receives a score of 2 on 3 items in a row. The last three 2s before the 1 or 2 become the basal level. The examiner begins testing with the entry point item. If the child does not score 2 on each of the first 3 items administered, that is, if the child scores 0 or 1 on any of the first 3 items administered starting from the entry point, the examiner should test backward until the child scores 2 on 3 items in a row. This is the basal level. All items below the basal level are scored 2.
- **Ceiling Level:** Once the basal level has been established, the examiner administers progressively more difficult items until a ceiling is established. The ceiling is established when the child scores 0 on each of 3 items in a row. After the ceiling has been established, testing is discontinued. All items above the ceiling are scored 0.

If a score of 2 for items below basal level or score of 0 for items above ceiling are not entered in the evaluation, they will be filled in according to the instruction of the manual.

For each visit and subtest:

- An “observed” value is an item with a recorded value in a subtest (e.g., 0, 1, 2 and Not Evaluated).
- Within a subtest, all items prior to the first item with an “observed” score are considered “Basal” and are assigned the score of 2.
- An empty item in a subtest surrounded by “observed” values (e.g., there are “observed” values prior to the item and after the item), the value is to be left empty and considered “observed”.
- All items after the last recorded value in a subtest, or “observed” value (e.g., 0, 1, 2 and “Not Evaluated”), are considered “Ceiling” values and are assigned a score of 0).

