6.2.10. Oculogyric Crisis

Episodes of oculogyric crisis (OGC) will be captured through paper or eDiary with specified questions.

Data from OGC diaries will be summarized in 2 ways:

1. Proportion of time and hours of OGC experienced per month
2. Frequency of OGC per month

The proportion of time for each subject will be calculated as total duration of all OGC episodes within the defined interval divided by total hours of that interval. Figures will be provided for the proportion of time and for the frequency of OGC per month.

If a subject did not have full month's record for a month at the beginning period prior to gene therapy or did not have full month's records for a month toward the end of the series of the

timepoints after gene therapy, the actual first date of reporting OGC in the diary (for prior treatment records) or the last date of reporting OGC in the diary (after treatment) for that month will be used to calculate total hours reporting OGC for that time period for that subject.

A listing of OGC data will be presented and will include start date and time, stop date and time, duration, medications taken, as well as pre-specified symptoms including uncontrolled eye movement, still limbs, lock jaw, neck dystonia, tongue thrust, trunk dystonia and overall assessment of severity.

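### The oculogyric crisis (OGC) diary is described as episode-only, so in months counted at full hours a stretch when it is not kept is scored as crisis-free; incomplete first and last months are bounded by OGC dates, and months without entries have no rule

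*SAP*

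**What the plan says.** **How episodes are captured.** Table 1 of protocol 7.1 has one diary row, "Oculogyric crisis eDiary instructions for use", marked at Screening only. Its footnote sets the duty: "Parent/caregiver must complete eDiary or paper diary for each OGC occurrence throughout the Trial Phase and Extension Phase". Protocol 7.3.6 says the same: "Oculogyric crisis episodes should be entered in the eDiary or paper diary when they occur". Table 2 has no diary row, but the footnote carries the diary through the Extension Phase, to Week 48.

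**How they are analysed.** SAP 6.2.10 gives two summaries. One is the proportion of time, "total duration of all OGC episodes within the defined interval divided by total hours of that interval". The other is "Frequency of OGC per month".

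**The exception for incomplete months.** The same section treats months at either end of the series differently. The condition at the start is: "If a subject did not have full month's record for a month at the beginning period prior to gene therapy". A parallel condition covers months toward the end of the post-treatment series. In the first case, hours run from the first date on which an OGC was reported. In the second, "the last date of reporting OGC in the diary (after treatment) for that month will be used to calculate total hours reporting OGC".

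**Missing data.** The general rule in SAP 4.3.1 is "Missing data due to missed visits or withdrawal or death will not be imputed". It does not mention diary gaps.

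**The concern.** An episode-only diary looks the same for a month with no crises and a month in which nobody wrote anything down. The main formula resolves that ambiguity one way: every hour of a full month is observed time, and hours without an entry are crisis-free.

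The design gives the ambiguity a direction. The comparison is before against after treatment in a single open-label arm. The pre-dose diary starts with instruction at Screening and covers roughly 2 to 10 weeks; the post-dose diary runs for 48 weeks. If reporting were less complete later than earlier, the OGC burden would appear to fall with no treatment effect, and no concurrent group would show the drift. With a minimum of 3 subjects, one caregiver can move the summary.

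Other planned data do not clearly fill the gap. Protocol 7.3.6 lists OGC among symptoms the investigator will evaluate. The footnotes to Tables 1 to 3, however, limit the visit assessment to hypotonia, dystonia and muscle power, and SAP 6.2.9 does not list OGC. Under protocol 7.5.2.1, a pre-existing condition is an adverse event only if it worsens or becomes more frequent.

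**Working it through.** The documents state no OGC rate, episode duration or diary compliance, so there is no figure to reproduce. The inputs below are assumptions chosen to show the mechanism.

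**Assumed inputs.** A 30-day month, H = 30 × 24 = 720 h; n = 8 episodes of d = 4 h; constant true burden 8 × 4 / 720 = 32/720 = 4.44%; reporting fraction c.

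**1. Months counted at full hours.** SAP proportion = c × n × d / H; frequency = c × n.

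| c | Proportion | Frequency per month | Apparent change |
|---|---|---|---|
| 100% | 4.44% | 8.0 | 0% |
| 90% | 4.00% | 7.2 | −10% |
| 80% | 3.56% | 6.4 | −20% |
| 70% | 3.11% | 5.6 | −30% |
| 50% | 2.22% | 4.0 | −50% |
| 30% | 1.33% | 2.4 | −70% |

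The relative fall is 1 − c whatever n, d and H are. Both summaries fall together, so the second is no check on the first. With 3 subjects at 4.44% and one caregiver reporting half, the mean becomes (4.44 + 4.44 + 2.22)/3 = 3.70%, an apparent fall of about 17%.

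**2. The same months with only diary-kept time in the denominator.** If the loss is whole stretches without a diary, observed hours shrink with the entries: c × n × d / (c × H) = 4.44% at every c. If instead single episodes are missed while the diary is otherwise kept, the hours do not shrink and this denominator recovers nothing.

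**3. Incomplete last month under the SAP exception.** Suppose 4 episodes of 4 h are recorded (16 h), the last on day 14, and the diary stops after day 15.
- All hours: 16/720 = 2.22%.
- SAP exception, bounded at day 14: 16/(14 × 24) = 16/336 = 4.76%.
- Bounded by the diary stop: 16/(15 × 24) = 16/360 = 4.44%.

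Here the exception prevents the dilution in step 1 and overshoots slightly.

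**4. Why the exception overshoots.** Its bound is an event date, so crisis-free time beyond that date is dropped. Place k episodes uniformly over 30 days with complete reporting and end the denominator at the last one. The average inflation factor, from simulation, is:
- k = 8: 1.12
- k = 4: 1.30
- k = 2: 1.87
- k = 1: 4.0

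The k = 1 value can be checked by hand: the mean of 30/m for m = 1 to 30 is 1 + 1/2 + … + 1/30 ≈ 4.0. Starting the denominator at the first episode date before treatment is the mirror image. It raises the pre-treatment value, towards apparent benefit; at the end of follow-up the exception raises the post-treatment value, against it. The fewer the episodes, the larger the distortion.

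**5. What no rule covers.** Three cases are open: gaps within middle months, months with no entries at all, and how a full month's record is to be recognised when only episodes are entered.

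**The case against.** The strongest objection is that the SAP does not divide by all hours throughout. A reader might infer that a caregiver who stops making entries is scored as 0% OGC time. The documents do not say so. If entries stop partway through a month at the end of the series, the exception cuts the denominator at the last OGC date, and step 3 shows that this works against apparent benefit. Later months with no entries are undefined, not defined as zero. This stands, and it limits the dilution argument to months counted at full hours and to gaps outside the exception.

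A reader might also infer that the diary has no way to record a crisis-free period. The diary questions are not reproduced, and the SAP's reference to a full month's record implies some notion of completeness, though none is defined. What can be said is that both protocol passages describe entry on occurrence only. Likewise, declining compliance is a possibility the plan leaves open; nothing in the documents shows that it will happen.

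The remedy has limits as well. A yes/no question asked up to four weeks later relies on recall by the same reporter. It removes stretches without a diary, not scattered forgotten episodes. It cannot be collected for contacts already past, and the protocol is at Version 11.0 with a history from 2020. In a very small study, setting intervals to missing may thin the summary and introduce selection. These points stand and are why the all-hours result should be kept alongside.

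Finally, OGC falls under AADC-specific symptoms among the secondary endpoints and is summarised descriptively, without a test. The SAP lists each episode with start and stop times, so a careful reader could spot gaps in entries. The listing still cannot say whether a gap was crisis-free.

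**Conclusion.** The concern holds in a limited form. In months counted at full hours, time when the diary was not kept is treated as crisis-free. Both OGC summaries fall in proportion to the loss: 20% at 80% reporting and 50% at 50%, on assumed reporting levels and a constant true burden. The direction matches benefit, and there is no control group.

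Incomplete first and last months have a separate flaw. The OGC-date bounds inflate the pre-treatment value, which favours apparent benefit, and the last post-treatment value, which opposes it. The net direction over the whole series cannot be determined from the documents. Months without entries need a rule before either summary is reproducible.

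The documents do not support the stronger reading that the reported OGC reduction will be an artefact of non-reporting. That would require falling compliance, empty months counted as zero and no confirmation item in the diary, and none of these is documented. No primary endpoint or test depends on this summary, so it is worth correcting at modest priority.

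**What to change.** First check the diary questions. If they already include a no-episode or completeness item, cite it in SAP 6.2.10 and build the denominator from it.

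Otherwise:
- **Collection.** Add one yes/no eCRF item asking whether the OGC diary was kept since the last contact and, if there are no entries, whether no OGC occurred. Ask it at Baseline and Day 1 for the pre-dose period, and at the contacts already scheduled from Week 2 to Week 48: Weeks 2, 3, 4, 6, 8 (5) plus Weeks 10, 12, 16, 20, 24, 28, 32, 36, 40, 44, 48 (11), 16 in all.
- **Denominator.** Use confirmed diary-kept time for both the proportion of time and the frequency.
- **Edge months.** Replace the first and last OGC dates with the dates on which diary-keeping started and stopped, so that two competing denominators do not coexist.
- **Empty months.** Count confirmed ones as zero and unconfirmed ones as missing.
- **Sensitivity.** Also show the all-hours result. It covers intervals already past for which confirmation was never collected.

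The cost is one question at existing contacts, one row in each of Tables 1 and 2, and a short rewrite of SAP 6.2.10. The downside is that some intervals become missing, the reported reduction may be smaller, and episodes forgotten within a confirmed interval are not recovered. If a new item is no longer practicable, the SAP can still define a full month's record, state how empty months are handled, and present the results with those months counted as zero and with them left out.

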6.2.11. Annual Rate of Respiratory Infection/Pneumonia

For pneumonia and respiratory infection, preferred terms under INFECTION and INFESTATION SOC selected for summary include the following:

- Bronchiolitis
- Bronchitis
- Pneumonia
- Pneumonia Haemophilus
- Pneumonia Influenzal
- Pneumonia Mycoplasmal
- Pneumonia Viral
- Respiratory tract infection
- Stenotrophomonas infection

Infections will be summarized as:

- Annual rate for all subjects after receiving gene therapy
- Annual rates prior to and after achieving head control (PDMS-2 score=2) for subjects who gained head control
- Annual rate after gene therapy for subjects who did not achieve head control.

Annual rate will be calculated using total time of all subjects in the study for that year as denominator and the total number of episodes of infection/pneumonia during that year as numerator:

$$\text{Annual rate} = (\text{total number of episodes during that year}) / (\text{total time for that year})$$

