8.3.3. Analysis of Secondary Endpoints

Observed values and change from baseline in the neurotransmitter CSF metabolites HVA, 5-HIAA, 3-OMD in CSF; brain ¹⁸F-DOPA PET; PDMS-2 total and subscale scores; Bayley-III cognitive and total language subscale scores; EQ-5D-Y scores; body weight; and AADC-specific symptoms will be summarized using descriptive statistics (count, mean, standard deviation, median, minimum, and maximum) or proportion as appropriate for each timepoint.

The number and percentage of subjects who achieve each motor milestone will be summarized by timepoint.

Oculogyric crisis diary data will be summarized by severity, frequency, and proportion and duration of time subjects experienced OGC during the study for selected timepoints, as appropriate.

Respiratory infection rate will be summarized over time.

TEAEs will be summarized as described in Section 8.3.2. The number of subjects who experience dyskinesia, number of dyskinesia episodes, median time to first episode, and summary statistics for duration of dyskinesia events will be provided.

Physical examination, vital signs, MRI, clinical laboratory values, T-cell, anti-AAV2 antibody values, and viral shedding will be summarized by visit, and shift table(s) will be provided if appropriate.

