10.1. Version 1.1: 24 March 2020

Overall reason for Version 1.1: The overall reason for this amendment was to incorporate feedback from FDA.

Item No.	Protocol Section	Amendment/Update	Reason/ Rationale
1	Protocol	Document date/version and abbreviations were updated; small grammatical and format changes were made throughout. Added pediatric to characterize study population.	Update
2	Synopsis, 2.3.2, 7.4, 8.3.4	Changed section to Exploratory Endpoints, and deleted AIMS, Bayley Scale of Infant Development, Gross Motor Function Measure, and Manual Ability Classification System.	Agency request
3	3.1	Added an interval of 3 weeks between successive subjects.	Agency request
4	Synopsis, 3.1, 7.1	Changed Part A and Part B to Trial Phase and Extension Phase.	Update
5	Synopsis, 4.1	Deleted former Inclusion Criterion 2, added new inclusion criteria for age, cranium development, lack of benefit from standard medical therapy, unable to ambulate independently, and laboratory values within normal pediatric range.	Agency request
6	5.3	Allow treatments for AADC deficiency throughout study duration as long as prespecified conditions are met.	Agency request
7	6.1	Added stopping rules.	Agency request
8	7.1	
Clarified hospitalization stay.Specified that PDMS-2 should be done at same time of day at baseline, 6 months, 12 months.Deleted AIMS, Bayley Scale of Infant Development, Gross Motor Function Measure, and Manual Ability Classification System.	Agency request
9	7.5.1	Added peri-operative safety monitoring measures.	Agency request

Item No.	Protocol Section	Amendment/Update	Reason/Rationale
10	7.5.2.2	Deleted sentence that an event need not be reported as an SAE if it exclusively represents a relapse of an expected change or progression.	Agency request
11	7.5.12	Added an independent pediatric neurologist to evaluate safety.	Agency request
12	Attachment 1	Added PDMS-2 score sheet.	Agency request

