Section 7.1	Activated partial thromboplastin time (aPTT) was added to the list of coagulation tests in the laboratory tests in the Schedule of Events for the Trial Phase and the Extension Phase.	Update.
Section 7.1, Section 7.3	A statement about Bioclinica performing central reads on PET scans was added.	Update.
Section 7.1, Section 7.3.3	The Bayley-III assessment was added to the Schedule of Events at Baseline, Visit 14, and Visit 20, and a description of the assessment was added.	Update.
Section 7.1, Section 7.3.4	The EQ-5D-5L was added to the Schedule of Events at Baseline, Visit 14, and Visit 20, and a description of the assessment was added.	Update.
Section 7.5.3.1	Language related to reporting AESIs related to the neurosurgical procedure to PTC Pharmacovigilance was revised to capture events specific to the neurosurgical procedure and not general risks associated with surgery. Other AEs that may occur during the surgical procedure will be captured as general AEs as described in Section 7.6.8.	This language was updated to ensure that risks associated specifically with the neurosurgical procedure are reported to PTC Pharmacovigilance.
Section 8.3	The General Approach section of the Statistical Methods and Data Analysis was updated to reflect changes to study assessments (Bayley-III, EQ-5D-5L, and body weight) in this amendment. Other revisions were made for clarity.	Update.

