4. GENERAL CONSIDERATIONS

Unless otherwise specified, continuous variables will be summarized by presenting the number of non-missing observations, mean, standard deviation, median, minimum, maximum, 25th percentile and 75th percentile.

Categorical variables will be summarized by presenting the number of subjects and percentage for each category.

All lab values that are reported as “< LLOQ” will be displayed in the listings as received but for summary statistics, this will be imputed as 0.5*LLOQ. For other laboratory values recorded as “< x.x” will be imputed as “x.x” minus 1 or other reasonable handling method as suggested by clinician for calculation.

When appropriate, study days will be listed in the data listings. For each subject, study day is measured relative to the day of study drug administration.

When data are summarized by visit, it will be based on nominal visit as shown on the case report form (CRF), and no date window will be applied. The site will be instructed to complete all assessments required for each study visit according to the schedule of assessments.

Analyses will be performed using SAS for Windows statistical software, version 9.4 or higher (SAS, Cary, NC), except where other software may be deemed more appropriate.

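### SAP 6.2.11 splits infection rates at head control, which is first re-measured at Week 24: the split can show a fall with no effect, and its denominator is not time in each state

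*SAP*

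**What the plan says.** Protocol 8.3.3 plans one thing: "Respiratory infection rate will be summarized over time". SAP 6.2.11 keeps an annual rate for all subjects after gene therapy and adds two rates defined by head control: "Annual rates prior to and after achieving head control (PDMS-2 score=2) for subjects who gained head control", and "Annual rate after gene therapy for subjects who did not achieve head control". For the calculation it states: "Annual rate will be calculated using total time of all subjects in the study for that year as denominator".

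SAP 6.2.11 gives no date of attainment, no start for the 'prior' period, and no rule for a child who already scores 2 at baseline. Such a child is possible, because Protocol 4.1 requires only inability to walk independently. The first and third rates are explicitly post-therapy; the prior/after pair is not, and adverse events are recorded from screening (Protocol 7.5.4).

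Protocol Table 1 has PDMS-2 once, at baseline. Later assessments are at Weeks 24, 48, 72, 96, 156, 208 and 260 (Tables 2 and 3). For data summarised by visit, SAP section 4 says "it will be based on nominal visit as shown on the case report form (CRF), and no date window will be applied".

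**The concern.** Children are grouped by something that happens later. A new gainer, meaning a child without a score of 2 at baseline, cannot be recorded as a gainer at a scheduled visit before Week 24. The weeks straight after neurosurgery therefore always count as 'prior', and all 'after' time comes later. With no control group (Protocol 1.3) and no age or time adjustment named in SAP 6.2.11, any background decline in infections would look like a consequence of head control. Separately, a rate for the time before or after an event needs the time spent in that state as its denominator, and the SAP names a different one. At stake is whether these rates can support a statement that children have fewer chest infections once they hold up their heads.

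**Working it through.** The plan states no infection rate, so there is no figure to reproduce. All rates below are assumptions, and head control has no effect unless stated.

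**1. When a gain can be dated.** Week 24 for the first repeat PDMS-2 is partly inferred, because the columns of Table 2 do not align reliably in the text copy. Week 24 (Visit 14) is an in-person visit. Two amendment-log entries, used only as support for timing, agree: "PDMS-2 should be done at same time of day at baseline, 6 months, 12 months" and, for the companion scale, "The Bayley-III assessment was added to the Schedule of Events at Baseline, Visit 14, and Visit 20". Visits 14 and 20 are Weeks 24 and 48. The longest nominal gap between assessments is 156 − 96 = 60 weeks.

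**2. Early excess.** Let the rate be *e* per year to Week 24 and 1 per year afterwards, with the gain recorded at week *T*. Using person-time in each state, counted from surgery and pooled over years:

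prior rate = [24*e* + (*T* − 24)] / *T*; after rate = 1.

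| *e* | *T* | Prior | After | Apparent fall |
|---|---|---|---|---|
| 2 | 24 | 48/24 = 2.0 | 1.0 | 50% |
| 2 | 48 | (48 + 24)/48 = 1.5 | 1.0 | 33% |
| 1.5 | 24 | 36/24 = 1.5 | 1.0 | 33% |
| 1.5 | 48 | (36 + 24)/48 = 1.25 | 1.0 | 20% |
| 1 (constant) | any | 1.0 | 1.0 | none |

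The fall shrinks for later gains: with *e* = 2 and *T* = 96, prior = (48 + 72)/96 = 1.25, a 20% fall.

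**3. Steady decline.** Let the rate fall by a fraction *d* per year. With *k* = −ln(1 − *d*), the mean rate between years *a* and *b* is [(1 − *d*)^*a* − (1 − *d*)^*b*] / [*k*(*b* − *a*)]. Take the gain at Week 24 (0.4615 years) and follow-up to Week 260 (5 years). For *d* = 20%, *k* = 0.2231:

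- prior = (1 − 0.9021)/(0.2231 × 0.4615) = 0.95
- after = (0.9021 − 0.3277)/(0.2231 × 4.5385) = 0.567
- ratio = 0.60

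For declines of 10% and 30% the ratio is 0.78 and 0.46; for no decline it is 1.00.

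**4. Late dating alone.** Suppose a true halving starts at week 12 but is recorded at Week 24. Prior = (12 × 1 + 12 × 0.5)/24 = 0.75 and after = 0.5, so the ratio is 0.67 instead of 0.50. This error works against showing a benefit.

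**5. The denominator read literally.** Suppose every child gains at Week 24, the rate is a constant 1 per year, and 'that year' means year since gene therapy. Dividing each state's episodes by the whole year's time gives:

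- Year 1 prior: 24/52 = 0.46
- Year 1 after: 28/52 = 0.54
- Year 2 after: 1.00

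A constant rate then looks like a rise. With 2 per year to Week 24, Year 1 prior becomes 48/52 = 0.92 and the other two figures are unchanged. None of the Year 1 figures is the rate in its state.

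**The case against.** The best defence is that little rests on this summary. Respiratory infection is not among the listed secondary endpoints. SAP 6.2.11 plans no test or model, and Protocol 8.1 disclaims formal hypothesis testing, with a minimum of 3 subjects. The all-subject annual rate is untouched by the split and satisfies the protocol. Listings of milestones and adverse events would let a reader rebuild the timing. All of that stands and limits the weight of the point. It does not make the two conditional rates readable as stated.

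Three stronger readings are tempting, and the documents do not support them.

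- *The contrasts are always biased toward benefit.* They are not. The documents give no infection rate, trend or post-surgical excess. A constant rate gives 1.00, late dating dilutes a real effect, and the literal denominator can produce a rise.
- *A child who leaves early can only be a non-gainer.* Protocol 3.3 and 6.2 require an early-termination visit with the full Week 48 or Month 60 assessments, which include PDMS-2. A leaver can be recorded as gaining at that visit, or may have gained before it. Leaving early shortens the opportunity and does not fix the group. A gain first recorded at that visit adds essentially no 'after' time.
- *The nine-term list makes every rate too low.* The wording is "preferred terms under INFECTION and INFESTATION SOC selected for summary include the following", which does not clearly close the list. Unlisted events lower a rate only if they occur and belong to the intended outcome. The terms lean toward pneumonia and lower-tract disease, as the section title suggests, so widening the list is a preference.

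**Conclusion.** The point holds in conditional form. The schedule places at least the first 24 post-surgical weeks of each new gainer in 'prior', and grouping by a later outcome confounds the before/after contrast with age and time since surgery. If infections decline over that time, the split can show a fall with no effect of head control: 33–50% for an assumed 2 then 1 per year, 20–33% for 1.5 then 1, in each case with gains recorded at Week 24 or 48. If the rate is constant there is no fall. These sizes rest on assumed rates, on 'prior' starting at surgery, and on state-specific person-time, which the SAP does not specify.

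The denominator problem needs no assumption about infection trends: as written, the prior and after figures are not rates in those states. Both defects are confined to a descriptive secondary summary and leave the HVA endpoint alone.

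**What to change.** Rewrite the head-control part of SAP 6.2.11 as follows.

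- Treat head control as a time-updated status for every treated subject. 'Not yet achieved' runs from gene therapy to the first PDMS-2 score of 2, and 'achieved' runs from then on. A subject who scores 2 at baseline is 'achieved' from the start.
- Divide episodes in each state by person-time in that state, and print both episodes and person-years.
- Report within intervals bounded by the PDMS-2 visits: Weeks 0–24, 24–48, 48–72 and 72–96, Week 96 to Month 36, then yearly. Show Weeks 0–24 separately, because new gainers have no 'achieved' time there.
- Replace the gainer/never-gainer split with this table, and keep the all-subject annual rate.

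Yearly strata would not be enough. With 2 per year to Week 24 and 1 after, and all gains at Week 24, Year 1 still shows 2.0 against 1.0. With half gaining at Week 24 and half at Week 48, Year 1 'not yet' is (0.5 × 0.923 + 0.5 × 1.385)/(0.5 × 0.462 + 0.5 × 0.923) = 1.67 against 1.0, a false 40% fall. Within PDMS-2 intervals both states cover the same follow-up, so a trend in time since surgery that all children share cancels and the no-effect ratio is 1.00 wherever both states are present. Differences between children who gain early and late remain, so the table is still descriptive.

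The cost is SAP wording and programming, with no new data. The downside is small cells. They exist already: 3 children gaining at Week 24 and followed to Week 260 give 3 × 24/52 = 1.38 person-years before and 3 × 236/52 = 13.6 after. Printing the counts makes that visible.
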